## STUDY SUMMARY

Study Title:	A feasibility study exploring the impact of a low Advanced Glycation End-product (AGE) diet on skin autofluorescence (SAF) levels in kidney transplant recipients.
Local Study Reference:	UHDB/2020/018
Study Design:	
This is a feasibility study consisting of 2 components:
 
 
1. A randomised controlled trial (RCT) to investigate the impact of a low AGE diet on SAF levels in kidney transplant recipients.
 
2. A nested qualitative interview study to assess the facilitators and barriers to adherence.
 

Study Participants:	Kidney transplant recipients who receive their transplant follow-up care at the Royal Derby Hospital
Planner Number of Sites:	Single site: The Royal Derby Hospital
Planned Sample Size:	
RCT  40 kidney transplant recipients. Participants will be randomized in an unrestricted 1:1 ratio in random varying block sizes using a computer-generated random number into two groups: a) standard diet (control group) or b) low-AGE diet (intervention group).
 
Nested Qualitative Study  A sample of (n=15) participants will be purposefully selected; n=10 from the intervention group and n=5 from the control group.

Treatment Duration:	6 months
Follow-Up Duration:	No follow-up
Planned Start Date:	1 st October 2021
Planned Recruitment End Date:	30 th December 2021
Planned Study End Date:	30 th December 2022
Research Question/ Aims:	
Does a low-AGE diet reduce SAF levels and improve cardiovascular health in kidney transplant recipients?
 
Specifically, this study will address:
 
 
• Whether it is possible to conduct an RCT of the dietary intervention compared to a standard diet for kidney transplant recipients.
 
• Determine whether the intervention is acceptable and participant views and experiences of the intervention.
 

## FUNDING AND SUPPORT IN KIND

Funder(s)	Financial and Non-Financial Support Given
British Renal Society c/o Executive Business Support [name]	Joint BRS/KCUK grant Total Funding = £18,787
Kidney Care UK [name]	Joint BRS/KCUK grant Total Funding = £18,787

## **ROLES & RESPONSIBILITIES**

### **Sponsor**

The Sponsor, University Hospitals of Derby & Burton NHS Foundation Trust, take on overall responsibility for appropriate arrangements being in place to set up, run and report the research project. A Division of Responsibilities between the Sponsor and the Chief Investigator (CI) will outline the delegation of certain responsibilities from the Sponsor to the CI.

### **Funder**

The study is funded by a joint research grant from the British Renal Society and Kidney Care UK

### **Study Management Committees**

#### Trial Management Group

The trial management group members are [name] Chief Investigator, [name] [name], [name] and [name]. The group will meet monthly to oversee the day-to-day management of the trial, including all aspects of the conduct of the trial. Any problems with study conduct and participating centres will be raised and addressed during TMG meetings.

## LIST OF ABBREVIATIONS

Define all unusual or ‘technical’ terms related to the study. Add or delete as appropriate to your study. Maintain alphabetical order for ease of reference.

AE	Adverse Event
AGE	Advanced glycation end-products
aPWV	Aortic Pulse Wave Velocity
BMI	Body mass index
CI	Chief Investigator
CKD	Chronic kidney disease
CRF	Case Report Form
ESKD	End-stage kidney disease
GCP	Good Clinical Practice
hsCRP	High-sensitive C reactive protein
ISF	Investigator Site File
ISRCTN	International Standard Randomised Controlled Trials
NHS	National Health Service
PI	Principal Investigator
PIS	Participant Information Sheet
RCT	Randomised Control Trial
REC	Research Ethics Committee
R&D	Research & Development
SAE	Serious Adverse Event
SAF	Skin autofluorescence
SGA	Subjective Global Assessment
SOP	Standard Operating Procedure
TMG	Trial Management Group
UHDB	University Hospitals of Derby and Burton NHS Foundation Trust

## PROJECT GANTT CHART

Task name	2021				2022			
	Qtr 1	Qtr 2	Qtr 3	Qtr 4	Qtr 1	Qtr 2	Qtr 3	Qtr 4
Finalise study protocol								
Prepare study documentation								
Complete ethics application								
Await REC/HRA and R&D approvals								
Eligibility assessment/screening								
Recruitment								
Data collection/Study procedures and assessments								
Qualitative study interviews								
Data collation, analyses and dissemination								
Trial Management Group meetings								
PPI meetings								

## STUDY PROTOCOL

### 1. BACKGROUND

Kidney transplantation is the optimal treatment option for end-stage kidney disease (ESKD). 35,823 adult patients had a functioning kidney transplant for ESKD in the UK on 31/12/2017, which represented 55.2% of the renal replacement therapy population. Transplantation is not only beneficial for the individual but also represents value to the greater health economy. The first year of care after a kidney transplant costs around £17,000 and £5,000 for every subsequent year compared to the average yearly cost of dialysis of £26,835 (UK Renal Registry, 2019).

Cardiovascular disease is the leading cause of death in persons with chronic kidney disease (CKD) including post-transplant. Whilst quality of life and clinical outcomes have improved in recent years, the survival of persons on dialysis remains poorer than that of many cancers. When compared to healthy subjects of the same age, persons receiving haemodialysis have a fivefold shorter life expectancy (Ardhanari et al., 2014). Reduced following kidney transplantation, this cardiovascular risk remains high with the greatest excess morbidity and mortality seen amongst youngest individuals (Jardine et al., 2011)

Advanced glycation end-products (AGEs) are a group of compounds formed by the non-enzymatic glycation of proteins, lipids or nucleic acids which progressively disrupt protein structure ultimately affecting tissue structure and function (Mallipattu et al., 2012). AGE formation in the body is increased by exposure to high glucose levels (in diabetes) and by inflammation and oxidative stress. In addition, AGEs may accumulate from exogenous sources including food (especially when cooked at high temperatures by baking, grilling, frying or roasting) and tobacco smoke (Uribarri et al., 2010; Arsov et al., 2014). AGEs are also produced normally in the body and their accumulation is a recognised manifestation of the normal aging process. Importantly, accumulation of AGEs has been highlighted as a risk factor associated with increased risk of cardiovascular mortality and morbidity (Meerwaldt et al., 2005; Shardlow et al., 2020).

The measurement of skin autofluorescence (SAF) is a validated non-invasive way to assess tissue accumulation of AGEs. SAF levels are a strong predictor of cardiovascular events in CKD (Shardlow et al., 2020) and of death and graft loss in transplant recipients (Hartog et al., 2006). Crowley et al. (2013) reported significantly lower SAF levels in kidney transplant recipients compared to persons on dialysis; however, these remained elevated when compared to the general population. In a small number of patients with pre-transplant measurements, a reduction in SAF was observed at a mean of 16 months post-transplant. However, there is still a lack of evidence in this area.

Due to the adverse outcomes associated with higher levels of SAF, several options focused on reducing the accumulation of AGEs have been proposed. One of these promising interventions is the reduction of dietary AGE intake. It has been suggested that cooking techniques that avoid very high temperatures such as poaching, steaming, stewing and boiling can significantly reduce the AGE content of food when compared to frying, broiling, grilling and roasting (Uribarri et al., 2010). Several randomized controlled trials (RCT) conducted in healthy overweight and/or obese volunteers

(Harcourt et al., 2011; Mark et al., 2014; Macías-Cervantes et al., 2015), persons with diabetes and the metabolic syndrome (Vlassara et al., 2002; Cai et al., 2004; Vlassara et al., 2016), and in those with CKD (Peppa et al., 2004; Vlassara et al., 2009) and performing peritoneal dialysis (Yacoub et al., 2017) have reported that restriction of dietary AGE intake is associated with a reduction in circulating AGE levels, suggesting that a low AGE diet may also be associated with a decrease in SAF.

## **2. RATIONALE**

A systematic review (Clarke et al., 2016) concluded there was evidence to suggest that dietary modification to reduce dietary AGE intake was promising as an intervention to reduce AGE accumulation, highlighting the potential benefits of a simple dietary intervention in the prevention and treatment of chronic conditions. However, they noted that most of the evidence regarding dietary modifications to reduce exogenous AGEs is of low quality highlighting the need for further studies, which was of interest as this simple intervention is unstudied in kidney transplant recipients.

## **3. OBJECTIVES AND OUTCOME MEASURES/ ENDPOINTS**

### **3.1. Objectives**

The aim of this study is to establish the feasibility of conducting a definitive RCT which will investigate whether a low AGE diet leads to reduced SAF levels and improves cardiovascular health in kidney transplant recipients.

This innovative proposal is designed to test the feasibility of answering the question:

Does a low AGE diet reduce SAF levels and improve cardiovascular health in kidney transplant recipients?

Specifically, this study will address:

- Whether it is possible to conduct an RCT of the dietary intervention compared to a standard diet for kidney transplant recipients.
- Whether the intervention is acceptable, and participant views and experiences of the intervention.

Specifically, this study will address the following:

- Eligibility, recruitment and dropout rates, with reasons for loss to follow-up.
- Proportion of eligible participants recruited.
- The suitability and sensitivity of outcome measures for use in a larger trial.
- The most appropriate primary outcome measure for use in a larger trial and completeness of data.
- Estimates of the effects of the intervention to inform a sample size calculation for a larger trial.
- The feasibility of health economic data collection and preliminary cost data collection and calculations.

- The feasibility of delivering the intervention to the population group.
- Fidelity and adherence with the intervention.
- Determine whether the intervention is acceptable and participant views and experiences of the intervention.

### **3.2. Outcome**

**Primary outcome:** SAF values at 6 months.

**Secondary outcomes:**

- Participant adherence to dietary intervention (achieving dietary AGE intake <8000 kilounits [kU]/day).
- Slope of SAF values over 6 months.
- Change in SAF values at 6 months.
- Change in weight over 6 months.
- Change in aortic pulse wave velocity (aPWV).
- Change in high-sensitive C reactive protein (hsCRP).
- Change in quality of life.

## **4. STUDY DESIGN**

This is a feasibility study consisting of 2 components:

1. An RCT to investigate the impact of a low AGE diet on SAF in kidney transplant recipients.
2. A nested qualitative interview study to assess the facilitators and barriers to adherence.

## **5. STUDY SETTING**

This study will take place within an NHS Renal outpatient setting at University Hospitals of Derby and Burton NHS Foundation Trust (UHDB).

## **6. ELIGIBILITY CRITERIA**

Potential participants will be kidney transplant recipients who receive their follow-up care with the Transplant team at UHDB.

### **6.1. Inclusion Criteria**

- Adults (>18 years) with a functioning (not on dialysis) kidney transplant.
- More than 12 months post-transplant.
- Able and willing to give informed consent.
- SAF levels above the general population mean value for age (Appendix 1).

## **6.2. Exclusion Criteria**

- Persons with dark skin colour (i.e. Fitzpatrick skin colour type 5-6).
- Persons with malnutrition (Subjective Global Assessment [SGA] score  $\leq 5$ ).
- Pregnancy or breast feeding or intending pregnancy.
- Active infection.
- Active rejection.
- Persons with learning difficulties.
- Prisoners.

## **7. STUDY PROCEDURES**

### **7.1. Recruitment**

#### **7.1.1. Patient Identification**

Identification and enrolment of participants from the existing kidney transplant recipient population at The Royal Derby Hospital will be undertaken by the Chief Investigator [name], a member of the transplant team.

Initial contact will be made during a routine follow-up appointment. The initial details of the study and Screening Participant Information Sheet (PIS) will be provided by the usual care team (which may include the researcher). Participants will then be given ample time during their appointment to ask questions and consider whether they wish to participate with screening. Having obtained consent to screen Chief Investigator [name], a member of the transplant team will measure a SAF level. SAF level results are obtained within 3-5 minutes.

Participants with a SAF that is above the general population mean for age will then be invited to participate in the study. The Participant Information Sheet will be provided for the participants to take home. Participants will then be given ample time to ask questions and consider whether they wish to participate before being re-contacted by the Chief Investigator. If they do wish to participate, a further visit scheduled on the same day as their next routine appointment will be arranged to obtain consent and undertake baseline assessments.

It will be explained to the potential participant that entry into the study is entirely voluntary and that their treatment and care will not be affected by their decision. It will also be explained that they can withdraw at any time. In the event of their withdrawal, it will be explained that their data collected so far cannot be erased and will be used in the final analyses where appropriate.

The participant's general practitioner will not be informed about the study because there are no implications for other aspects of treatment.

Participants will not be paid to participate in the study. Travel expenses will be offered for any hospital visits in excess of usual care. The majority of study assessments will be timed to take place at the time of routine visits, treatment or assessment.

### **7.1.2. Screening**

Patient details will be assessed against the inclusion and exclusion criteria. Only those who meet the inclusion criteria and without exclusion criteria will be invited to participate.

At the initial contact visit outlined above, Chief Investigator [name], a member of the transplant team, will seek consent to measure SAF levels (i.e. consent to screen). Only patients with an SAF value that is above the general population mean for age will be invited to participate.

### **7.2. Consent**

Consenting of participants will be undertaken by the Chief Investigator [name], or an appropriately trained and delegated member of the research team.

The process for obtaining participant informed consent will be in accordance with the Research Ethics Committee (REC) guidance, Good Clinical Practice (GCP) and any other regulatory requirements that might be introduced. The Investigator has training and experience in assessing participant capacity and gaining informed consent in the clinical context.

Detailed information will be provided on the study to ensure that participants understand the purpose and potential risks involved. All participants will provide written informed consent. The Informed Consent Form will be signed and dated by the participant before they enter the study. The Investigator will explain the details of the study and provide a PIS, ensuring that the participant has sufficient time to consider participating or not. The Investigator will answer any questions that the participant has concerning study participation.

The decision regarding participation in the study is entirely voluntary. The Investigator or their nominee shall emphasize to them that consent regarding study participation may be withdrawn at any time without penalty or affecting the quality or quantity of their future medical care.

Informed consent will be obtained from each participant before they undergo any interventions related to the study. Informed consent must be obtained prior to the participant undergoing procedures that are specifically for the purposes of the study (including the collection of identifiable participant data). One copy of this will be kept by the participant, one will be kept by the Investigator, and a third will be retained in the participant's hospital records.

The Principal Investigator (PI) retains overall responsibility for the informed consent of participants at their site and must ensure that any person delegated responsibility to participate in the informed consent process is duly authorised, trained and competent according to the REC approved protocol and applicable guidelines and regulations.

### **7.3. The Randomisation Scheme**

Participants will be randomised in an unrestricted 1:1 ratio in random varying block sizes using a computer-generated random number into two groups: a) standard diet (control group) or b) low

AGE diet (intervention group). Advice regarding both diets will be provided by an experienced dietitian. Both groups will receive precise oral and written instructions on how to follow the diets. Dietary advice will be individualised to patients' food preferences.

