##### **7.3.1. Method of Implementing the Allocation Sequence**

The system to be used to coordinate randomisation is [www.sealed envelope.com](http://www.sealedenvelope.com)

The Chief Investigator, [name] and [name] [name] will be aware of allocation which will be documented in the CRF (paper).

There is no expectation that randomisation codes will need to be accessed out-of-hours or in an emergency.

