#### **10.3.2. Outcome Analysis**

Summary measures of all baseline variables will be calculated and reported. Primary and secondary outcomes will be compared between the two groups (Low AGE Diet vs. Standard Diet) at 6 months using a t-test if data are normally distributed or a Mann Whitney U test if not. Analysis will be by intention to treat.

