#### **10.4. Subgroup Analyses**

Due to the limited number of participants, we will conduct only a single subgroup analysis by evaluating the results in participants with and without diabetes. Since diabetes is relatively common in kidney transplant recipients and may be a dominant factor affecting SAF in these people, it would be important to investigate whether a low AGE diet is effective in people with diabetes.

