#### **10.5. Adjusted analyses**

As this is a feasibility study, we do not plan to conduct adjusted analyses.

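### Diabetes, which the protocol calls possibly dominant for SAF and makes its only subgroup, is controlled neither at allocation nor in the analysis of 40 people

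*Combined protocol and SAP*

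**What the plan says.** **Allocation.** Section 7.3 states: "Participants will be randomised in an unrestricted 1:1 ratio in random varying block sizes". The study summary repeats this. Section 7.3.1 names an online randomisation service but no stratification factor. No section provides for minimisation.

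**Diabetes.** Section 10.4 says that "diabetes is relatively common in kidney transplant recipients and may be a dominant factor affecting SAF in these people", and that "we will conduct only a single subgroup analysis by evaluating the results in participants with and without diabetes".

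**Analysis.** The primary outcome (3.2) is the SAF value at 6 months, not its change from baseline. Section 10.3.2 compares the arms "at 6 months using a t-test if data are normally distributed or a Mann Whitney U test if not". Section 10.5 adds: "As this is a feasibility study, we do not plan to conduct adjusted analyses".

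**Use of the estimate.** Section 3.1 lists, among the study's objectives, estimating the intervention effect to support the sample size of a larger trial. Section 10.1 gives the planning figures: 40 recruited, SD 0.64 AU, a difference of 0.6 AU, and 80% power with 18 per group.

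**The concern.** The protocol singles out one patient characteristic as likely to matter for the primary outcome and then leaves it to chance at both points where it could be controlled. Random blocks keep the arm totals close. They do nothing to balance diabetes within the arms. With about 20 people per arm, a visibly uneven split is not rare. Because the primary outcome is the raw 6-month value, SAF differences between people with and without diabetes that were present at entry pass straight into the arm comparison.

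Two things are at stake. One is the effect estimate that will be carried into planning the definitive trial. The other is the precision of the only subgroup contrast, which suffers when one arm holds few people with diabetes.

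**Working it through.** **1. The plan's own figure.** Inputs from Section 10.1: difference 0.6 AU, SD 0.64 AU, alpha 0.05 (taken as two-sided), power 80%.

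n per group = 2 × (1.96 + 0.8416)² × 0.64² / 0.6² = 17.9, so 18. Allowing for 10% drop-out, 36 / 0.9 = 40. Both stated figures reproduce. The same inputs in an exact t-test calculation give power 0.78 at 18 per group.

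**2. Chance of imbalance.** Prevalence is not in the documents, so I assume D = 8, 12 or 16 people with diabetes among 40 (20%, 30%, 40%). With 20 per arm, the number in one arm is hypergeometric (40, D, 20).

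| D of 40 | P(arms differ by ≥4) | P(arms differ by ≥6) |
|---|---|---|
| 8 | 0.235 | 0.044 |
| 12 | 0.301 | 0.082 |
| 16 | 0.333 | 0.105 |

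**3. Shift in the arm difference.** Shift = (difference in diabetes proportion) × (SAF effect of diabetes). The effect is also not given; I assume 0.3-0.6 AU.

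- 8 v 4: 4/20 = 0.20, so the shift is 0.06-0.12 AU, or 10-20% of the 0.6 AU target.
- 9 v 3: 6/20 = 0.30, so the shift is 0.09-0.18 AU, or 15-30% of the target.

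**4. Yardstick.** Standard error at 18 per group = 0.64 × √(2/18) = 0.213 AU, a 95% half-width of about 0.43 AU. The 8 v 4 shift is therefore roughly 0.3-0.6 of a standard error.

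**5. Long-run validity.** In a simulation of 18 per group with no stratification (30% prevalence, diabetes effect 0.4 or 0.6 AU, total SD held at 0.64), the unadjusted t-test rejected a true null 5.0% of the time.

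**6. Subgroup of people with diabetes (12 in total).** The variance of the arm contrast is proportional to 1/n₁ + 1/n₂.

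- 8 v 4 against 6 v 6: (1/8 + 1/4) / (1/6 + 1/6) = 1.125.
- 9 v 3 against 6 v 6: (1/9 + 1/3) / (1/6 + 1/6) = 1.33.
- Power for 0.6 AU with a perfect 6 v 6 split is 0.31.

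**7. Gain from adjusting for diabetes.** At 30% prevalence, R² = 0.3 × 0.7 × effect² / 0.64², and residual SD = 0.64 × √(1 − R²).

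| Assumed effect (AU) | R² | Residual SD (AU) | Power at 18 per group |
|---|---|---|---|
| none (unadjusted) | 0 | 0.640 | 0.78 |
| 0.3 | 0.05 | 0.625 | 0.80 |
| 0.4 | 0.08 | 0.613 | 0.81 |
| 0.6 | 0.18 | 0.578 | 0.86 |

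These powers ignore the degree of freedom spent on the covariate. They count diabetes only. Any gain from baseline SAF is extra and cannot be sized from the documents.

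**8. Is diabetes status available at allocation?** Section 7.4 draws medical history, including diabetes, from records and a baseline questionnaire after consent. The schedule in 7.5 places randomisation under Recruitment and participant characteristics under Baseline, a later column. The transplant team checks patient details at screening (7.1.2), so the information should be within reach, but the protocol does not show it being recorded before allocation.

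**The case against.** **Simple blocked allocation is a legitimate choice.** This stands. The test holds its size over repeated randomisations. Nothing in Section 10.1 suggests that variation due to diabetes was taken out of the 0.64 AU, so chance imbalance is presumably already reflected in the standard error. A reader might infer that the primary comparison is biased or invalid; the documents do not support that.

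**The size is assumed.** This also stands. Section 10.4 says only that diabetes may be dominant. Entry requires SAF above the mean for age (6.1), which could narrow the contrast between people with and without diabetes. The upper assumption of 0.6 AU equals the whole target difference. Even so, the 8 v 4 shift stays well inside one standard error.

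**Other parts of the plan help.** They do so partly. Change and slope of SAF are secondary outcomes and would remove imbalance already present in baseline SAF. Baseline variables will be summarised by arm, so an imbalance could be seen if diabetes is tabulated. Within each subgroup, diabetes cannot confound the diet comparison; imbalance there costs precision only. None of this alters the primary outcome, which is the 6-month value.

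**Why diabetes and not age?** Appendix 1 shows mean reference SAF rising from 1.53 AU at 20-29 years to 2.73 AU at 70-80. This is a fair point, and it favours putting baseline SAF in the model, which covers age and diabetes to the extent that they act through it.

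**It is only a feasibility study.** That limits the weight of the point but does not remove it. Section 3.1 makes the effect estimate a stated product of the study.

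**Conclusion.** The point holds as a low-cost improvement in design and analysis. The factor that the protocol itself picks out is uncontrolled at allocation and in the analysis. On assumed prevalences of 20-40%, a difference of at least 4 diabetic participants between arms has probability 24-33%. On an assumed effect of 0.3-0.6 AU, a 4-person difference shifts the result by 0.06-0.12 AU against a standard error of about 0.21 AU. That is a moderate distortion of a single realised estimate together with some lost precision, not an error in the test.

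Two stronger readings should be avoided. Stratifying would not rescue the subgroup analysis, which has power of about 0.31 for 0.6 AU even when 12 people with diabetes split evenly. Nor do the documents establish that diabetes status is already recorded before allocation, so stratification needs a small procedural step as well as a system setting.

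**What to change.** **Allocation (7.3 and the study summary).** Delete *unrestricted*, which also sits badly with blocking, and stratify the blocked randomisation by diabetes (yes/no) using small varying blocks in the online service already named. State how diabetes is defined for this purpose, and that status is confirmed from the medical record before allocation. Amend the order in the 7.5 schedule to match.

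**Analysis (10.3.2 and 10.5).** Replace the unadjusted t-test or Mann-Whitney comparison of 6-month SAF with a linear model (ANCOVA) containing arm, diabetes stratum and baseline SAF. All three are already collected. If the randomisation is left unchanged, this adjustment alone still captures most of the gain.

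**Cost.** One setting in the randomisation system, one check before allocation, and text changes in the summary, 7.3, 7.5, 10.3.2 and 10.5. Arm totals may differ by a few because of incomplete blocks in each stratum, and the model uses one or two degrees of freedom. In return, at an assumed 30% prevalence and 0.3-0.6 AU effect, adjusting for diabetes alone raises power at 18 per group from 0.78 to about 0.80-0.86.
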